#### 5.2 **Exclusion Criteria**

A subject meeting any of the following exclusion criteria is NOT eligible for participation in the study.

### Pre-operative:

- 1. Subjects admitted for trauma surgery.
- 2. Subjects unwilling to receive blood products.

- 3. Subjects with known history of severe (e.g., anaphylactic) reaction to blood products.
- 4. Subjects with known history of intolerance to any of the components of the IP.
- 5. Female subjects who are pregnant, breastfeeding or, if of child-bearing potential (i.e., adolescent), unwilling to practice a highly effective method of contraception (e.g., oral, injectable or implanted hormonal methods of contraception, placement of an intrauterine device or intrauterine system, condom or occlusive cap with spermicidal foam/gel/film/cream/suppository, male sterilization, or true abstinence) throughout the study.

True abstinence: When this is in line with the preferred and usual lifestyle of the subject. (Periodic abstinence [e.g., calendar, ovulation, symptothermal, postovulation methods], declaration of abstinence for the duration of a trial, and withdrawal are not acceptable methods of contraception.).

- 6. Subjects previously enrolled in clinical trials with FS Grifols.
- 7. Subjects currently participating, or during the study is planned to participate, in any other investigational device or medicinal product study.

### Intra-operative:

- 8. An appropriate parenchymous or soft tissue TBS (as defined in exclusion criteria 9 and 10) cannot be identified intra-operatively by the investigator (the surgeon).
- 9. The TBS has Grade 3 (severe) bleeding according to the investigator's (the surgeon's) judgment that cannot be controlled with conventional surgical techniques to Grade 1 or Grade 2 bleeding. The intensity of the bleeding at the TBS will be rated by the investigator using the 5-point validated bleeding severity scale (see Table 7-1).
- 10. The TBS is in an actively infected surgical field.
- 11. Occurrence of major intra-operative complications that require resuscitation or deviation from the planned surgical procedure.
- 12. Application of any topical hemostatic agent on the resection surface of parenchyma or soft tissue prior to application of the IP.

#### 5.3 **Subject Withdrawal Criteria**

Subjects have the right to withdraw from the study at any time for any reason, either before or after the surgical procedure. The investigator can withdraw a subject from the study at any time.

The investigator will document the reason(s) for withdrawal of each subject in source documents and in the eCRF. All data gathered on the subject prior to termination will be made available to the sponsor.

### 5.3.1 Screen Failures

Screening evaluations will be used to determine the eligibility of each subject for enrollment. Subjects who fail to meet eligibility criteria during screening, pre-operative, and intra-operative evaluations will be considered screen failures and will not participate in the study.

### 5.3.2 Removal of Subjects

Subjects may withdraw or be withdrawn from the study for the following reasons:

- 1. The subject withdraws informed consent at his/her own request or at the request of the legally authorized representatives (e.g., parent or legal guardian).
- 2. The subject does not meet all inclusion criteria (other than intra-operative) and is deemed a screen failure.
- 3. The subject does not meet the intra-operative inclusion criteria and is deemed a screen failure.
- 4. The subject meets any of the exclusion criteria (other than intra-operative) and is deemed a screen failure.
- 5. The subject meets the intra-operative exclusion criteria and is deemed a screen failure.
- 6. The subject is not able to adhere to the main protocol requirements (major protocol deviations).
- 7. The occurrence of an adverse event (AE) which in the investigator's opinion requires the withdrawal of the subject from the study.
- 8. The subject is lost to follow-up.
- 9. Subject's death.
- 10. Any event which in the opinion of the investigator impedes the subject's participation in the study.

For subjects who are screen failures or discontinued from the study early, study completion procedures will be completed as per Section 7.2.1.5.

If the reason for early discontinuation is due to an AE, in so far as was possible, the subject will be followed-up until the event resolves, or is stabilized, and no further change is expected.

In all cases, the reason for withdrawal must be recorded in the eCRF and in the subject's records.

### 5.3.3 Subject Replacement

Subjects who are randomized and treated with any amount of study drug and withdrawn from the study will not be replaced.

#### 5.3.4 Follow-up of Subjects Withdrawn from Study

Subjects who receive any amount of IP and discontinue early from the study will be requested to return for the Post-operative Day 30 Visit procedures within 7 days of the subject's withdrawal from the study.

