#### 8.3.8 Adverse Event Documentation

All AEs and SAEs occurring after the subject has signed the ICF through the final study visit (i.e., Post-operative Day 30±7 days) must be fully recorded in the subject's eCRF, and paper SAE report form (if serious) as well as in the medical record. If no AE has occurred during the study period, this should also be indicated in the eCRF.

It is the responsibility of the investigator to ensure that AEs are appropriately recorded.

At each visit, AEs will be elicited by asking the individual a non-leading question such as "Do you feel different in any way since the last visit?" Moreover, AEs will also be collected through directly observed events or spontaneously volunteered by the subject. Clearly related signs, symptoms, and abnormal diagnostic procedures should preferably be grouped together and recorded as a single diagnosis or syndrome wherever possible.

The following variables must be recorded in the AE eCRF:

- The verbatim term (a diagnosis is preferred)
- Date/time of onset
- Date/time of resolution
- Severity (mild, moderate, severe)
- Causality (unrelated, possibly related, definitely related)\*
- Seriousness (yes, no)
- Action taken (with regard to study treatment)
- Other action (to treat the event)
- Outcome and sequel (follow-up on AE)

In addition to the investigator's own description of the AEs (verbatim term), each AE will be encoded according to the Medical Dictionary for Regulatory Activities (MedDRA®).

\*Causality assessment will be made only when the AE occurs after the subject has received the study treatment. An AE occurring before subject's exposure to study treatment will be always labeled as "unrelated".

For example, a laboratory test abnormality considered clinically relevant (e.g., causing the subject to withdraw from the study, requiring treatment or causing apparent clinical manifestations) or judged clinically relevant in the context of the subject's medical condition by the investigator, should be reported as an AE. Each event must be described in detail along with start and stop dates, severity, relationship to IP, action taken and outcome. Each event must be adequately supported by documentation as it appears in the subject's medical or case file

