#### 8.3.9 Reporting of Serious Adverse Events

#### 8.3.9.1 Reporting of Serious Adverse Events

[figure not shown]
Any SAE (see Section 8.3.7) that occurs after signing the study ICF through the final study visit (i.e., Post-operative Day 30± 7 days) must be expeditiously reported whether or not considered attributable to the study treatment. Each SAE must be fully recorded in the subject's eCRF and additionally reported in a timely manner using the paper SAE Report Form.

SAEs will be reported using the designated paper SAE Report Form. When the investigator becomes aware of an SAE, she/he must submit a completed, signed and dated paper SAE Report Form (in English) within 24 hours to the sponsor by email/fax.

The date of this SAE discovery by the site staff should be documented in the source documents (i.e., medical records).

Each SAE must be followed up until resolution or stabilization. After the initial report, all relevant information for SAE follow-up, and for the outcome, must also be supplied to the sponsor in a timely manner (within 3 days from its identification or within 24 hours for relevant new information) by means of the paper SAE Report Form. In addition, the sponsor or contract research organization may request additional information and/or reports.

All paper SAE Report Forms must be reported to Grifols via email to:

When required, and according to local law and regulations, SAEs must be reported to the IRB/EC and regulatory authorities.

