# 8.4 Type and Duration of the Follow-Up of Subjects after Adverse Events

In so far as is possible, all individuals will be followed up until the AE or suspected ADR has been resolved. If an AE/suspected ADR/SAE is present when the subject has completed the study, the course of the event must be followed until the final outcome is known, or the event has been stabilized and no further change is expected and the investigator decides that no further follow-up is necessary.

Any SAE that occurs after the end of the clinical study or after study completion due to early termination will not be actively collected. However, if such cases are reported by an investigator as potentially related to the study treatment, they will be entered into the safety database for expedited purposes. Conversely, if the investigator considers the event not related to the study treatment, then it will be considered a non-case.

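### In treated children withdrawn early, new adverse events between the brought-forward final visit and Post-operative Day 30 are not actively sought

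*Protocol*

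**What the plan says.** Study product is applied only during the operation, and none may be applied after the 4-minute assessment (Protocol 6.1, 6.4). A treated child may later leave the study for several reasons under 5.3.2. These include a major protocol deviation, any event the investigator thinks impedes participation, and "The occurrence of an adverse event (AE) which in the investigator's opinion requires the withdrawal of the subject from the study".

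For treated subjects who discontinue early, 5.3.4 says they "will be requested to return for the Post-operative Day 30 Visit procedures within 7 days of the" subject's withdrawal. Section 5.3.2 sends the same subjects to 7.2.1.5, which is headed Day 30 ± 7.

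On collection of events:

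- Section 8.2.1 runs AE collection to the last day of the subject's participation.
- Section 8.3.8 covers "All AEs and SAEs occurring after the subject has signed the ICF through the final study visit" and equates that visit with Post-operative Day 30 ± 7. Section 8.3.9.1 does the same for SAE reporting.
- Section 8.4 states: "Any SAE that occurs after the end of the clinical study or after study completion due to early termination will not be actively collected". It makes an exception "if such cases are reported by an investigator as potentially related to the study treatment": those cases enter the safety database.

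On existing events, 5.3.2 says that after discontinuation for an AE, as far as possible, "the subject will be followed-up until the event resolves, or is stabilized, and no further change is expected". Sections 8.3.9.1 and 8.4 likewise require SAEs, and any event present at completion, to be followed to an outcome or stabilisation.

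In the analysis, a treatment-emergent AE is one between the start of treatment and the final visit (Protocol 9.1.3.1, SAP 10.1).

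**The concern.** Early withdrawal usually has two parts: stopping treatment and stopping observation. Here treatment is over before the child leaves the operating room, so post-operative withdrawal stops only observation. Bringing the last assessment forward therefore shortens the search for new events, with no treatment decision that requires it.

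The safety objective is reported as incidence of treatment-emergent events in the Safety population. A child last seen on Day 10 stays in the denominator with the same weight as one seen on Day 30. Section 7.2.1.5 uses the Day 30 visit to look for bleeding-related complications, and 2.3.2 names thromboembolic events as a risk. A new event of either kind after the early visit could go unrecorded.

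The sections also give sites two answers. Section 5.3.4 ties the visit to the withdrawal date, while 7.2.1.5, 8.3.8 and 8.3.9.1 tie it, or the collection period, to Day 30 ± 7.

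**Working it through.** The plan states no figure on this point that could be reproduced. The check is day arithmetic plus a reading of the collection rules.

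**Inputs.** The final visit window is Day 30 ± 7, that is Day 23 to Day 37 (8.3.8, 8.3.9.1). The visit after early withdrawal falls within 7 days (5.3.4). The plan has 86 subjects per arm (9.2).

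**Formula.** For withdrawal on post-operative day w, the latest permitted visit is day w + 7. The smallest shortfall is max(0, 23 − (w + 7)) to the start of the window and max(0, 30 − (w + 7)) to nominal Day 30. If the visit takes place on the day of withdrawal, replace w + 7 by w.

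| Withdrawal day | Latest visit | Days short of 23 / 30, latest visit | Days short of 23 / 30, same-day visit |
|---|---|---|---|
| 1 | 8 | 15 / 22 | 22 / 29 |
| 3 | 10 | 13 / 20 | 20 / 27 |
| 7 | 14 | 9 / 16 | 16 / 23 |
| 10 | 17 | 6 / 13 | 13 / 20 |
| 14 | 21 | 2 / 9 | 9 / 16 |
| 16 | 23 | 0 / 7 | 7 / 14 |
| 23 | 30 | 0 / 0 | 0 / 7 |

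**Thresholds.** w + 7 < 23 gives w < 16, and w + 7 < 30 gives w < 23. So the rule forces the visit ahead of the window only for withdrawal before Day 16, and ahead of Day 30 only before Day 23. For later withdrawals an earlier visit is permitted but not forced.

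**What is collected after the early visit:**

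1. An event already present: still followed (5.3.2, 8.3.9.1, 8.4).
2. A new SAE that the investigator reports as potentially related: entered in the safety database (8.4). It is outside the treatment-emergent window if the final visit is the early one.
3. A new SAE considered unrelated: a non-case if 8.4 applies to the individual subject. During participation, 8.3.9.1 asks for every SAE regardless of attribution.
4. A new non-serious AE: no section asks for it once participation has ended (8.2.1).

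**Scale of one event.** If 86 children per arm are treated, one missed event is 1/86 = 1.2 percentage points in that arm.

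**The case against.** The strongest reply is that the children who most need follow-up are already protected. A reader might infer that safety follow-up is cut off in children withdrawn for an adverse event. The documents do not support that. Section 5.3.2 has a rule for this group, and 8.3.9.1 and 8.4 add to it; none of them stops at Day 30. This part of the objection stands. It does not close the gap for new events: a child withdrawn on Day 3 for an event that has resolved by Day 10 has no further planned contact.

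A reader might also infer that SAE information ceases altogether. It does not, because of the exception in 8.4. Nor does 8.4 say whether *early termination* means the subject's or the study's, and 4.6.2 uses similar language for the study. If it means the study's, 8.2.1 still ends collection with the subject's participation.

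Third, if the final study visit in 8.3.8 and 8.3.9.1 means calendar Day 30 ± 7 for everyone, the gap shrinks. That reading is open, but it sits badly with 5.3.4, and sites could follow either.

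Two further inferences are not supported. The documents give no withdrawal rate, so no count of affected children can be derived. They also do not show that loss would differ by arm: 4.3.3 blinds the sponsor and states no masking of the surgeon, which makes a difference possible, not shown.

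Finally, SAP 5 already summarises discontinuation after treatment by reason. That shows who left early, but not how long each child was observed.

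**Conclusion.** The point holds in a limited form. After any early withdrawal of a treated child, new-onset AEs and SAEs between the early final visit and Post-operative Day 30 are not actively sought, and they fall outside the treatment-emergent window. This applies whatever the reason for withdrawal.

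For withdrawal on Day 3, the unobserved time is 13 days to Day 23 or 20 days to Day 30 with the latest permitted visit, and 7 days more with a same-day visit. The forced gap disappears for withdrawal from Day 16 (against Day 23) or Day 23 (against Day 30). The overall effect on reported incidence cannot be computed.

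The conclusion assumes that the final visit of a withdrawn child is the one in 5.3.4 and that participation ends there. It is a cheap improvement to safety follow-up. It does not touch the primary efficacy analysis, which ends at closure of the surgical field.

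**What to change.** - **Protocol 5.3.4:** continue AE/SAE collection in treated, withdrawn children to Post-operative Day 30 ± 7, unless consent for follow-up is withdrawn, the child is lost to follow-up, or the child dies. Make the Day 30 contact at that time, by telephone if a visit is not possible.
- **Protocol 5.3.2, 7.2.1.5, 8.2.1, 8.3.8, 8.3.9.1 and 8.4:** reconcile these with the amended 5.3.4. State what the final study visit means for a withdrawn subject, and whether *early termination* in 8.4 refers to the subject or the study.
- **SAP:** report by arm the number of treated children whose AE follow-up ended before Day 23.

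The cost is protocol wording, a few more follow-up contacts and one table row.

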#### 6 TREATMENT OF SUBJECTS

See Section 4.4 for the treatment(s) to be administered, including the name(s) of all the product(s), the dose(s), the dosing schedule(s), and the route/mode(s) of administration.

### 6.1 Administration and Timing of Investigational Products for Each Subject

The initial volume of the study treatment to be applied at the TBS should be sufficient to entirely cover the intended application area by a thin, even layer.

For each subject 2 years of age or older randomly assigned to be treated with FS Grifols or EVICEL, the maximum total volume of IP allowed to be applied at the TBS will be 12 mL.

For each subject less than 2 years of age randomly assigned to be treated with FS Grifols or EVICEL, the maximum total volume of IP allowed to be applied at the TBS will be 6 mL.

FS Grifols or EVICEL will be applied via either drip or spray applicator for soft tissue TBS and via spray applicator only for parenchymous tissue TBS.

The IPs are for topical/epilesional use only.

- For subjects  $\leq 2$  years old, randomized to the FS Grifols treatment group, up to 6 mL of FS Grifols solution will be allowed per subject; and for subjects  $\geq 2$  years old, up to 12 mL of FS Grifols solution will be allowed per subject. For subjects in the FS Grifols treatment group, the initial volume of FS Grifols to be applied to the TBS should be sufficient to entirely cover the intended application area by a thin, even layer. For every subject in the soft tissue type, FS Grifols will be administered by dripping or spraying onto the TBS surface according to the investigator's judgment. For every subject in the parenchymous tissue type, FS Grifols will be administered by spraying onto the TBS surface. Before any application of FS Grifols to the TBS, it is recommended to remove accumulated blood from the surrounding tissues and the target area to be treated according to normal practice in order to have a dry field prior to application of FS Grifols (e.g., by means of suction, sponges or sterile gauzes). If FS Grifols is applied by dripping, the tip of the applicator should be kept as close to the tissue surface as possible without touching the tissue during application. If FS Grifols is applied by spraying, the recommended distance between the spray applicator and the surface of the target area is at least 2 cm. The time of the start of the initial IP application (TStart) and the time of the end of the initial IP application (TEnd) will be recorded.
- For subjects  $\geq 2$  years old, randomized to the EVICEL treatment group up to 12 mL of EVICEL solution will be allowed per subject; and for subjects  $\leq 2$  years old, up to 6 mL

	Number	BIG-CL-PRT-000005	Version	5.0	Status	Effective	Effective Date	11-Nov-2021
CIVILO	IG1405 - A F	Prospective, Randomized, Active-Contro	ılled, Single-k	olind, Parallel	Group Clinical	Trial to Evaluate the	Base	V 2 30 C V
Bioscience Industrial Group	Safety and E	fficacy of Fibrin Sealant Grifols (FS Gri	fols) as an Ac	djunct to Haer	nostasis durin	g Surgery in	r aga	4 / 10 64

of EVICEL solution will be allowed per subject. For subjects in the EVICEL treatment group, the initial volume of EVICEL to be applied to the TBS should be sufficient to entirely cover the intended application area by a thin, even layer. For every subject in the soft tissue type, EVICEL will be administered by dripping or spraying onto the TBS surface according to the investigator's judgment. For every subject in the parenchymous tissue type, EVICEL will be administered by spraying onto the TBS surface. Spray or drip EVICEL in short bursts (0.1-0.2 ml) onto the tissue to produce a thin, even layer. The amount of EVICEL required depends upon the area of tissue to be treated and the method of application. If EVICEL is applied by dripping, the tip of the applicator should be kept as close to the tissue surface as possible without touching the tissue during application. Individual drops should be applied to the surface area to be treated and the drops should be allowed to separate from each other and from the tip of the applicator. If the applicator tip becomes blocked, the yellow catheter tip should be wiped clean or cut back in 0.5 cm increments. If EVICEL is applied by spraying, the distance between the nozzle and the tissue surface should ideally be between 10 and 15 cm when spraying in open surgery. Spray pressure that is within the recommended guidelines by the device manufacturer should be maintained (e.g., an air pressure of 20-25 psi [measured by airflow]) and insufflation pressure in all such procedures should be monitored (2). The time of the start of the initial IP application (TStart) and the end of the initial IP application (TEnd) will be recorded.

- If the hemostatic effect is incomplete after TStart and before the primary efficacy endpoint at T4, additional amounts of IP may be applied at the TBS up to the maximum allowed volume of 12 mL for subjects greater than or equal to 2 years of age and 6 mL for subjects less than 2 years of age if necessary. It is recommended to remove accumulated blood from the surrounding tissues and the target area to be treated according to normal practice in order to have a dry field prior to application of IP (e.g., by means of suction, sponges or sterile gauzes). These additional applications of IP should be performed via spray or drip application as per the investigator's judgment for soft tissue type and via spray application for parenchymous tissue type. The time of start (TStart2) and end (TEnd2) of IP re-application will be recorded. No additional amounts of IP may be applied beyond the primary efficacy endpoint assessment time point at T4.
- The approximate total amount of IP applied to the TBS and the method(s) of administration (drip or spray) will be documented.
- Subjects in the either treatment group should not receive any alternative hemostatic product or treatment (including application of manual pressure) during the 10-minute observational period, apart from re-application of IP before the primary efficacy endpoint at T4, unless there is Grade 3 or 4 (see Table 7-1) breakthrough bleeding at the TBS that jeopardizes subject safety according to surgeon's judgment, in which case the surgeon may use any other hemostatic measure at his/her discretion (the use of FS Grifols, EVICEL, or other plasma-derived hemostatic agents are not allowed in this case). In this case, the subject will be considered a treatment failure. The alternative treatment applied will be recorded in subject's source documents and eCRF.
- IP can only be applied to the TBS in this study.

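### Protocol Section 6.1 places a 2-year-old under both the 6 mL and the 12 mL maximum volume, in both arms

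*Protocol*

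**What the plan says.** All four statements are in Protocol Section 6.1.

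- **Opening paragraphs, both arms.** The 12 mL limit is introduced with "For each subject 2 years of age or older randomly assigned to be treated with FS Grifols or EVICEL, the maximum total volume of IP" and the 6 mL limit with "For each subject less than 2 years of age randomly assigned to be treated with FS Grifols or EVICEL, the maximum total volume of IP". Age 2 belongs to the first group only.
- **FS Grifols bullet.** The lower limit is given as "For subjects $\leq 2$ years old, randomized to the FS Grifols treatment group, up to 6 mL of FS Grifols solution", and the same sentence continues "for subjects $\geq 2$ years old, up to 12 mL of FS Grifols solution will be allowed per subject". Age 2 belongs to both groups.
- **EVICEL bullet.** For subjects aged 2 and above, "randomized to the EVICEL treatment group up to 12 mL of EVICEL solution will be allowed per subject"; the sentence continues "and for subjects $\leq 2$ years old, up to 6 mL". Age 2 again belongs to both groups.
- **Reapplication bullet, both arms.** The ceiling is "12 mL for subjects greater than or equal to 2 years of age and 6 mL for subjects less than 2 years of age". Age 2 belongs to the 12 mL group only.

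No other section supplied sets a limit by age for this trial. Section 6 sends the reader to Section 4.4 for doses, but Section 4.4 gives kit and package sizes. Section 2.4.1 describes limits in the earlier trials. SAP Section 8.2 summarises the volume applied without stating a limit.

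**The concern.** A maximum volume in children should have one value at each age. Here the instructions for each product give two values at age 2, and one of the two disagrees with the general paragraphs and with the reapplication bullet. Two sites could apply different ceilings to the same child and each point to a sentence that supports them.

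Two things are at stake. The first is safety: the documents do not say unambiguously how much plasma-derived product a 2-year-old may receive. The second is the classification of deviations. Per Protocol membership (Protocol Section 9.5, SAP Section 4.2) depends on major deviations that could affect the primary endpoint, settled at a data review meeting before unblinding. For a 2-year-old given more than 6 mL, that meeting would have two rules to choose from.

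**Working it through.** **Step 1. Apply each statement at ages around the boundary.** The inputs are the four statements in Section 6.1, with the inequality signs as they appear in the text supplied. Entries are the maximum in mL.

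| Statement in Section 6.1 | 23 months | Age 2 | 3 years |
|---|---|---|---|
| Opening paragraphs | 6 | 12 | 12 |
| FS Grifols bullet | 6 | 6 and 12 | 12 |
| EVICEL bullet | 6 | 6 and 12 | 12 |
| Reapplication bullet | 6 | 12 | 12 |

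Below age 2 and at age 3 all four agree. The conflict is confined to age 2 and to the two product bullets.

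**Step 2. Size of the discrepancy.** 12 / 6 = 2. For FS Grifols that is two kits against one, since Section 4.4.3 describes a 6 mL kit. Any volume above 6 mL and up to 12 mL meets one limit and exceeds the other. For example, 8 mL is within the 12 mL limit and is 8 / 6 = 1.33 times the 6 mL limit.

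**Step 3. Who is covered.** Section 6.1 does not define how age is counted.

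- *Exact age.* A child of 25 months is 25 / 12 = 2.08 years, which is above 2, so every statement gives 12 mL. Only a child at exactly 2 years is caught, at most those recorded as 2 years 0 months.
- *Completed years.* Every child from 24 to 35 months counts as 2 and falls under both limits.

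Protocol Section 7.2.1.1 records age in years and months, and SAP Section 7.1 derives age from both. Neither says which reading governs the volume limit. On either reading the conflict has a practical effect only if more than 6 mL is applied. The documents give neither the number of 2-year-olds expected nor a distribution of volumes.

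**Step 4. What is not touched.** mITT membership requires meeting the intra-operative criteria and receiving any amount of product (Protocol Section 9.5), and the primary endpoint (Section 7.1.1) has no volume component. The power statement in Section 9.2 uses response rates of 80% in each arm, 86 subjects per arm and a ratio margin of 0.80. On the log scale, SE = sqrt(2 × (0.2 / 0.8) / 86) = 0.0762, and power = Φ(0.2231 / 0.0762 − 1.96) = 83.3%. This agrees with the stated figure of at least 80%, and no input to it is a volume.

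**The case against.** The strongest reply is that the conflict rests on two non-strict signs, one in each product bullet, and that the statements written out in words agree with each other. Signs of this kind are doubtful elsewhere in the machine-read text:

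- The time-to-hemostasis bands in Protocol Section 9.1.2 and SAP Section 9.3 overlap at their endpoints.
- SAP Section 9.1 puts equality in both the null and the alternative hypothesis.
- Protocol Section 7.1.1 defines rebleeding as above Grade 1, where Sections 4.1.1 and 7.2.1.3.3 and SAP Section 3.1.1 say Grade 1 or above.

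A strict sign could have been misread in both bullets. This objection stands as a reason to check the original PDF first and to hold moderate confidence. It does not dispose of the point, because the text as supplied contradicts itself.

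A second reply is that the opening paragraphs, the reapplication bullet and the randomization strata (Section 4.3.2) all separate the ages without overlap, so a reader can infer what was meant. That inference may be reasonable, but a site should not have to infer a paediatric maximum from sentences that disagree.

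A third reply is that the consequences are limited. A volume deviation removes a child from the Per Protocol set only if it is judged major and relevant to the primary endpoint, and the primary analysis uses mITT. That is correct, and it keeps the statistical effect small.

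**Conclusion.** As the text stands, Section 6.1 contradicts itself for a subject aged 2, in both arms, by a factor of two in the maximum volume. It is a safety ambiguity in operative instructions, with a possible effect on Per Protocol membership. Confidence is moderate, because the finding assumes that the signs are the same in the original PDF.

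Four stronger readings are tempting, and the documents do not support them.

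- *The youngest children have no clear limit.* Every statement gives subjects under 2 the same 6 mL limit.
- *The overlap favours one arm.* The limits and the age overlap are the same for FS Grifols and EVICEL, so the wording builds in no imbalance in dosing.
- *The main result is at risk.* The mITT analysis and the power do not depend on the volume applied.
- *A definite number of children is affected.* Section 9.2 plans 50 to 100 children aged 2 to 11 years. Spread evenly over ten yearly ages, that gives 50 / 10 = 5 to 100 / 10 = 10 two-year-olds. The even spread is an assumption, and the figure also needs the completed-years reading. It counts every 2-year-old, whereas only those given more than 6 mL matter. On exact age the number is close to zero.

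**What to change.** 1. Check the inequality signs in the FS Grifols and EVICEL bullets against the original PDF. If they prove to be strict below age 2, the point falls away.
2. If the overlap is confirmed, reconcile the opening paragraphs, the two product bullets and the reapplication bullet so that every age has exactly one maximum. State how age is counted, so that the boundary cannot be read two ways.
3. Use that same boundary when volume deviations are classified for the Per Protocol set, and settle it before the data review meeting.

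Which limit applies to a 2-year-old is for the sponsor to decide. Importing the cut used for the randomization strata would in effect make that choice, so it should not be treated as a mere matter of wording.

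The cost is a protocol wording correction and a clarification letter to sites. No additional data or subjects are needed. SAP Section 8.2 already estimates the total volume applied for each arm, so applications above 6 mL can be identified from data that will be collected anyway.
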